10.3.4. According to protocol (ATP) cohort for efficacy

The ATP cohort for efficacy will include all subjects included in the TVC with no major protocol deviations that are determined to potentially interfere with the efficacy assessment of the study vaccine and contributed to the time at risk starting 14 days after the third dose. The membership in this study population will be determined in a blinded fashion at a data review meeting attended by the sponsor Medical Officer, the site PI/Co-PI, and the sponsor Statistician, and the list of criteria used to exclude subjects from the ATP cohort for efficacy, including vaccine or anti-malarial administration and other relevant analysis protocol deviations, will be finalized before database freeze.

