7. STUDY PROCEDURES

7.1. Study procedures and evaluations

7.1.1. Study specific procedures

This is a Phase 2b, single-center, open label, randomized controlled trial with five groups in one study site. 619 adults will be enrolled. It is assumed that 90% will complete study procedures and be evaluable. Prior to study start, a community information program will inform the local population of the study and study information will be presented at community centers. Screening procedure timelines for any single subject will include a 12-day window period before randomization. Data collection will be by CRF. Following the Screening Phase, trial-specific procedures are sub-divided into 3 separate Epochs. Epoch 1 describes the procedures during the Treatment and Immunization Phase (Appendix B). Epoch 2 describes the procedures during the Active Detection of Infection Phase (Appendix C). If insufficient number of PCR-positive events to meet both the primary and secondary endpoints occur during Epoch 2, it will be necessary to extend the ADI for an additional 24 weeks (Epoch 3, Extension Phase, Appendix D) (refer to Statistical Section 10).

A. Study-specific Screening Procedures (Appendix A)

Screening procedures are to be completed as shown in Appendix A. Screening (day -39 to day -28) may be done on a separate visit from recruiting. Only adults aged 18 to 55 years with a signed/thumb printed and dated Informed Consent document will be eligible to be screened for the trial. At the screening visit each subject will be given a Subject Screening Number (only to be used for screening) and each will have a clinic record prepared.

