designated as the first positive PCR for *P. falciparum* malaria during an ADI phase (either Epoch 2 or 3). If all events are achieved while all subjects are in Epoch 2, then visit 27 will be the final study visit and subjects will not continue into Epoch 3.

Subjects will be seen at KCRC or visited by field workers or community health workers (CHW) every 21 days during the ADI period per the schedule in Appendix C. At each contact for ADI a sample of whole blood will be collected by finger stick into EDTA-coated tubes (at KCRC a venous blood sample can be collected in cases where a finger prick sample cannot be collected). In the case of field visits, samples are then transported back to KCRC for processing. Approximately 350 to 500 μ L of whole blood will be collected at each ADI visit. For all subjects an aliquot (approximately 250 μ L) will be placed on DBS cards. If the subject has not yet had a positive PCR sample obtained during the ADI phase, then approximately 100 to 250 μ L blood will be sent for PCR testing. Subjects with a positive PCR during the ADI phase will have their results recorded in the CRF. Subjects with a prior positive *P. falciparum* PCR will continue to have finger prick blood samples for DBS collected every three weeks until the end of Epoch 2. Such samples may be used in a future exploratory study under a separate protocol in order to genotype parasites that are identical to or dissimilar from the *P. falciparum* parasite 3D7 strain used in the RTS,S vaccine. All subjects will return for visit 27 where groups 1 – 3 will have serology assessment and all subjects will have a whole blood sample collected (optimally by finger stick) for parasitemia assessment (both DBS and PCR regardless of if they have had prior positive PCR during ADI). Note: only a participant's first positive PCR during ADI will be counted as an endpoint.

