8.4.4. Reporting of Pregnancy

Subjects who become pregnant during the study must not receive additional doses of investigational study vaccines but may continue other study procedures at the discretion of the investigator. The investigator, or his designee, will collect pregnancy information on any subject who becomes pregnant while participating in this study. The investigator, or his designee, will record pregnancy information on the Pregnancy Report Form and submit it to the WRAIR IRB, KEMRI SERU, Kenya PPB, PATH, and GSK. In

the event a woman becomes pregnant after completing all three vaccinations she will be eligible to continue in the ADI phase. If a pregnant female develops asymptomatic malaria infection discovered by a positive malaria PCR during ADI, she will be treated with standard of care malaria therapy.

The subject will be followed to determine the outcome of the pregnancy. At the end of the pregnancy, whether that be full-term or premature, information on the status of the mother and child will be forwarded to the above ethical committees, regulatory authorities and sponsor for reporting.

While pregnancy itself is not considered an AE or SAE, any pregnancy complication or elective termination of a pregnancy for medical reasons will be recorded as an AE or a SAE. A spontaneous abortion is always considered to be a SAE and will be reported.

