10.5. Sample Size

This is a Phase 2b study to assess the vaccine efficacy of RTS,S in adults in a malaria endemic region. The statistical analysis will measure vaccine efficacy using Cox proportional hazards regression (time to first PCR-positive infection). An attack rate of 40% over 6 months has been assumed as a conservative estimate in an epidemiologic setting of perennial transmission in Western Kenya. A fixed vaccine efficacy of 50% is a conservative assumption according to the estimated vaccine efficacy.

Using an event-based design and assuming 10% drop out of the enrolled population and a one-sided $\alpha=0.025$, the following are power and required number of events to conduct the analysis:

Table 9. Sample Size Calculations

Power	N to enroll per group	Total events required to conduct analysis	Endpoint
90%	164	92	Primary (Group 1 vs 4)
80%	128	72	Secondary (Group 2 vs 5)

The impact of the event-driven design is that we will continue to follow up until 92 events have been observed in aggregate between Groups 1 and 4 of the ATP cohort for efficacy, and 72 events have been observed in the aggregate of Groups 2 and 5 of the ATP cohort for efficacy. If the aggregate numbers of events have been reached prior to 24 weeks of ADI, study actives will continue to occur through the end of Epoch 2 only (though some subjects may have begun Epoch 3 as discussed in 7.1.1). If the aggregate number of events during Epoch 2 does not reach the cutoff indicated in Table 9, then the ADI will be extended up to 48 weeks or until the total number of events is reached, whichever occurs first. This will require the PCR lab to provide timely aggregated reports of event counts (across Group 1 plus 4; and Group 2 plus 5) and may result in more than the required events for either the primary or secondary endpoint.

An additional cross-sectional PCR will be performed at the Study Termination Visit as described in section 7.1.1, but these PCR results will not count toward the study endpoints.

Based on these assumptions we estimate a greater than 90% probability of observing the required number of events for the primary and secondary analyses by 6.9 months. However, larger dropout rates and/or a lower attack rate will extend the amount of follow-up time necessary to accumulate the required number of events.

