APPENDIX I. DETAILED ROLES AND RESPONSIBILITIES

The **Principal Investigator (PI)** will be responsible for ensuring the protocol is executed as written, obtaining consent, conducting physical examinations and medical histories, determining eligibility of an individual to participate in the study, collecting data, data analysis, protocol design, administrative support, adverse event reporting, observation of participants, progress/continuing review reporting, briefing volunteers, clinical care of participants, review of source documents, randomization, investigational product accountability, overseeing all other research activities, documenting protocol deviations, training and supervising study staff, and delegating responsibilities as appropriate. The **Co-Principal Investigator (Co-PI)** will have the same responsibilities as the PI and can serve as an alternate in decision making if the PI is unavailable. However, if there are any disagreement between the Co-PI and the PI, the ultimate authority for a decision will rest with the PI.

The **Associate Clinical Investigators**, as delegated by the PI, may be responsible for executing the protocol as written, obtaining consent, conducting physical examinations and medical histories, determining eligibility of an individual to participate in the study, collecting data, data analysis, protocol design, assist in supervising study staff, administrative support, adverse event reporting, observation of participants, progress/continuing review reporting, briefing volunteers, clinical care of participants, review of source documents, overseeing research activities, and any other study activities as delegated by the PI.

The **Clinical Research Coordinator**, as delegated by the PI, may be responsible for executing the protocol as written, collecting data, data analysis, protocol design, administrative support, coordinating all protocol activities, maintaining essential trial documents, adverse event reporting, scheduling participant appointments, reviewing source documents, drug accountability, randomization (though will not have access to manual randomization envelopes), quality assurance/control, overseeing research activities, and any other study activities as delegated by the PI.

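### Section 10.3.4 says ATP membership for efficacy is decided blind, but the site PI/Co-PI of this open-label trial attends, so blinding of that judgement cannot be assured; a minor second point is that the cohort behind the 92/72-event trigger is not named consistently

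*Protocol*

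**What the plan says.** **Who decides membership.** Section 10.3.4 admits to the ATP cohort for efficacy those TVC subjects who contribute time at risk from 14 days after dose 3 and have no major deviation judged capable of interfering with the efficacy assessment. Membership is "determined in a blinded fashion at a data review meeting attended by the sponsor Medical Officer, the site PI/Co-PI, and the sponsor Statistician". The list of exclusion criteria "will be finalized before database freeze"; no earlier date is given.

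**What the site knows.** Section 7.1.1: "This is a Phase 2b, single-center, open label, randomized controlled trial with five groups in one study site". Appendix I gives the PI "review of source documents, randomization, investigational product accountability, overseeing all other research activities, documenting protocol deviations", and gives the Co-PI the same responsibilities. Positive PCR results go into the CRF (7.1.1 C).

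**Where the set is used.** Sections 10.4.2 and 10.4.3 assign both efficacy Cox models to this cohort.

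**The event trigger.** Section 10.5 continues follow-up "until 92 events have been observed in aggregate between Groups 1 and 4 of the ATP cohort for efficacy", and likewise to 72 in Groups 2 and 5. Section 4.2 gives the same counts for the pooled groups, names no cohort and refers to 10.5. Section 7.1.1 C and D speak of events among all subjects; 7.1.1 D also speaks of the ADI groups and refers to 10.5/Table 9. Sections 4.2 and 10.5 both say that the PCR laboratory will report aggregated counts.

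**The concern.** Deciding by judgement who enters the primary analysis set is acceptable when those who judge know neither arm nor outcome. Here one attendee's role gives access to both. The criteria may stay open until shortly before database freeze, by which time the events have occurred. If exclusions lean on that knowledge, even unintentionally, the estimated vaccine efficacy can shift in either direction, and randomization no longer protects the comparison.

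The trigger matters for a different reason. It decides who enters Epoch 3 and when ADI ends, so everyone applying it needs the same count, and that count must be obtainable during follow-up. The laboratory's reports as described carry no ATP status, and membership is settled only at the data review meeting.

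**Working it through.** **1. Blinding: the passages side by side.**

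- Arm: the trial is open label, and the PI/Co-PI role covers randomization and product accountability (7.1.1, Appendix I).
- Outcome: site procedures depend on each subject's PCR status. Blood goes for PCR only "If the subject has not yet had a positive PCR sample obtained during the ADI phase" (7.1.1 C). Epoch 3 visits are for subjects without an event (7.1.1 D). Section 8.4.4 has treatment of pregnant women depend on an infection "discovered by a positive malaria PCR during ADI".
- Evidence: the same role documents the deviations that the meeting judges.
- Discretion: whether a deviation could interfere with the efficacy assessment is partly a judgement.

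Listings without group codes may be what is meant by blinded. They would not mask a person who can already know arm and result. The protocol gives no exclusion rate or pattern, so the selection risk cannot be put into numbers.

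**2. Trigger: Table 9 reproduces.** Inputs from 10.5: HR 0.5, one-sided 0.025, 40% attack rate over 6 months, 10% dropout. Allocation is 1:1 (10.5.1).

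- Expected events, 0.9 × N × (0.40 + 1 − 0.60^0.5): N = 164 gives 92.3; N = 128 gives 72.0.
- Freedman power, Φ(√d/3 − 1.96): d = 92 gives 89.2%; d = 72 gives 80.7%.
- Schoenfeld power, Φ((√d/2)·ln 2 − 1.96): 91.4% and 83.7%.

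The numbers are sound. Only the cohort they refer to is unclear.

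**3. Effect of an all-subject count.** The simulation used 164 and 128 per arm, uniform enrolment over 6 months, control hazard −ln(1 − attack rate)/182.6 per day, and detection at the next scheduled visit. Those visits fall on days 0 and 14 and then every 21 days, counted from study day 211. Everyone completes Epoch 2 (161 days). Extension runs until both thresholds are met or until day 329, the last Epoch 3 visit.

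The protocol gives no ATP exclusion rate. I assume 10%, random and independent of arm, either on top of the planned 10% dropout or fully overlapping it. Section 7.1.1 allows the overlap: "It is assumed that 90% will complete study procedures and be evaluable".

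| Attack rate | ATP events, added / overlapping | Freedman power, primary | Freedman power, secondary |
|---|---|---|---|
| 40% | 90.7 and 70.9 / 95.2 and 74.3 | 88.6–90.0% | 79.9–81.7% |
| 30% (assumed) | 87.0 and 67.7 / 87.4 and 68.2 | about 87% | about 78% |

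The largest Freedman losses at 40% are 89.2 − 88.6 = 0.6 point and 80.7 − 79.9 = 0.8 point. At 30% the loss is 2 to 3 points.

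**4. Effect of an ATP count.** Mean end of ADI, in days from the first subject's Visit 19:

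- At 40%: 347 against 344 with the exclusion added, and 344 against 344 with overlap, so 0 to 3 days later. No run in 2,000 fell short of 92 or 72.
- At an assumed 30%: 393 − 356 = 37 days later (overlap) to 454 − 392 = 62 days later (added). ATP events still fall below 92 in roughly 1–15% of runs and below 72 in roughly 2–20%, because ADI reaches its maximum length first.

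**The case against.** **On blinding.** The PI/Co-PI attends but is given no casting decision, and two sponsor roles are present. The endpoint is a laboratory PCR, and only major deviations count. Being able to know a subject's arm is not the same as recalling arm and result for 584 ADI-group subjects (619 − 35). All of this limits the likely harm. None of it makes the review blinded, and it does not separate the person documenting the deviations from the judgement on them. A reader might infer that the whole meeting is unmasked or that the ATP set will be biased. The documents support neither: nothing suggests that the sponsor's attendees know allocation, and harm is possible but not shown.

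**On the trigger.** Section 10.5 is the specific rule, and 4.2 and 7.1.1 D point to it. The phrase about all subjects plausibly contrasts the aggregate with the individual; taken literally it would include Group 3, which has no ADI. This largely stands, and ATP is probably meant. A reader might also infer that an ATP count is impossible during follow-up. That goes too far, because deviations are recorded as they occur and a CRO manages the data. What remains is that no passage links the laboratory's counts to ATP status.

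**On the SAP.** A full exclusion list, and a sensitivity model in the total cohort for efficacy (10.3.6), are ordinary SAP content. Their absence here is not part of this point. A SAP would not, however, correct the protocol's own statement about blinding or align its trigger wording.

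**Conclusion.** The main point holds. The only set named for the efficacy models rests on a partly discretionary exclusion step described as blinded, although an attendee can know arm and PCR result and documents the deviations. Blinding of that step cannot be assured. The size of any resulting selection cannot be derived from the document. Because the remedy is cheap and protects the primary comparison, it should be made.

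The trigger point is real but minor: inconsistent wording, and no stated route from laboratory counts to ATP events. At the protocol's 40% attack rate and VE of 50%, with an assumed 10% ATP exclusion, an all-subject count costs at most about one point of power. A reader might infer a larger loss by taking 10% off exactly 92 and 72: 82.8 and 64.8 events, with Freedman power of about 86% and 77%. The protocol does not support that calculation, because everyone must complete Epoch 2 and 4.2 and 10.5 both foresee more events than required. The loss of 2 to 3 points needs the further assumption of a 30% attack rate.

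**What to change.** **ATP membership (10.3.4).** Fix objective exclusion rules before the first ADI visit (Visit 19). Apply them by program, or by staff without access to arm and PCR results. Limit the PI/Co-PI to supplying the facts of each deviation, and remove the statement that their review is blinded.

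**Trigger (4.2, 7.1.1, 10.5).** Name the ATP cohort for efficacy in all three places. Have the data management CRO combine PCR and deviation data under the pre-fixed rules and release only the two pooled counts, Groups 1 plus 4 and Groups 2 plus 5.

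**Cost.** Changed wording in four sections and one counting program, with no new data items. The price in follow-up time is the delay in step 4 of the working: negligible at the planned attack rate, and one to two months if the rate is nearer 30%, where a shortfall also remains possible.

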10.3.5. ATP cohort for immunogenicity

The ATP cohort for immunogenicity will include all subjects included in the TVC who received all vaccinations according to protocol procedures and within the protocol specified intervals, performed blood samplings for immunogenicity according to protocol intervals, and did not use any medication or blood products forbidden by the protocol and did not have any reported underlying medical condition influencing immune responses.

10.3.6. Total cohort for efficacy

The total cohort for efficacy includes all TVC subjects who receive all three doses of RTS,S/AS01_E vaccine or comparator and contributed to the time at risk starting 14 days after the third dose.

10.4. Description of Statistical Methods

10.4.1. General Approach

A positive PCR for the presence of *P. falciparum* parasites meets the definition of an event if the result is obtained from a blood sample collected at any time during the ADI phase of the trial (Epoch 2 or 3).

10.4.2. Analysis of the Primary Efficacy Endpoint

Vaccine efficacy against the first PCR-positive *P. falciparum* infection among adults who were *P. falciparum* positive at baseline will be assessed using Cox proportional hazards regression with a covariate for group assignment to compare Groups 1 and 4. The vaccine efficacy estimates (1-hazard ratio), 95% CI, and p-values will be calculated from this model. Cumulative incidence graphs will also be provided. This analysis will be conducted in the ATP for efficacy cohort.

